# B. Secondary Outcome(s)

DOSE REQUIREMENT: Median twice-daily enoxaparin dose, as measured in mg/kg, required to achieve a 4 hour post-dose anti-factor Xa level of 0.20-0.49 anti-Xa U/mL.

EXPLORATORY EFFICACY: Proportion of plasma D-dimer levels <2x ULN; cumulative incidence of VTE; and duration of assisted ventilation.

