#### 2. Inclusion Criteria

#### Inclusion Criteria for COVID-19 Infected Patients:

- 1. Children (birth to <18 years of age)
- 2. Positive nucleic acid test, antigen testing, or antibody testing for SARS-CoV-2 within the past 7 days
- 3. Hospitalized <72 hours post-admission
- 4. One or more signs and/or symptoms of COVID-19 illness within the past 72 hours, as follows:
  - i.) Cough
  - ii.) Fever (oral temperature >100.4°F/38°C)
  - iii.) Chest pain
  - iv.) Shortness of breath
  - v.) Myalgia
  - vi.) Acute unexplained loss of smell or taste
  - vii.) New/increased supplemental oxygen requirement
  - viii.) Acute respiratory failure requiring non-invasive or invasive ventilation
  - ix.) Encephalitis
- 5. Clinical suspicion that the above symptoms are related to COVID-19 infection and not an alternative etiology.

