1. STUDY OBJECTIVES

1.1. SPECIFIC AIM 1

- To investigate the safety of in-hospital thromboprophylaxis with twice-daily low-dose enoxaparin thromboprophylaxis (starting dose, 0.5 m/gkg subcutaneously q12 hours, adjusted to achieve a 4 hour post-dose anti-factor Xa level of 0.20-0.49 anti-Xa U/mL) in children hospitalized with COVID-19 related-illnesses, as measured by the cumulative incidence of ISTH-defined [10] clinically-relevant bleeding (primary endpoint).

1.2. SPECIFIC AIM 2

- To determine the median twice-daily enoxaparin dose, as measured in mg/kg, required to achieve a 4 hour post-dose anti-factor Xa level of 0.20-0.49 anti-Xa U/mL in children hospitalized with COVID-19 related-illnesses, and to compare dose-requirements by age group (birth to <1 year old, 1-<6 years old, 6-<13 years old, and 13-<18 years old).

1.3. SPECIFIC AIM 3

- To investigate, on an exploratory basis, the efficacy of in-hospital thromboprophylaxis with twicedaily enoxaparin in children hospitalized with COVID-19, as measured by the proportion of serial D-dimer levels obtained at standardized time points that are <2 times the upper limit of normal (<2x ULN) values for age (Aim 3a; surrogate marker of efficacy), the cumulative incidence of radiologically-confirmed HA-VTE (Aim 3b; clinical efficacy), and the median duration of in-hospital increased respiratory support (new requirement for high-flow nasal cannula, non-invasive ventilation, and/or mechanical ventilation, relative to any at-home baseline requirement; Aims 3c, clinical efficacy).

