2.5. SAMPLE SIZE

The study enrolled 38 participants

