3.3. EXPLORATORY OUTCOMES

Proportion of plasma D-dimer levels <2x ULN; cumulative incidence of VTE; and duration of assisted ventilation (Mechanical ventilation, Non-invasive ventilation and Extracorporeal life support).

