4.1.2. Baseline data

The flow of patients, including the overall eligible patients, excluded patients and patients in the analytic dataset will be presented in a Figure (Figure 1). We will present demographic and clinical characteristics for all patients and by age (<12 and >=12 years) and MISC status (Table 1). Continuous variables will be summarized as means with standard deviations or medians with observed range or interquartile range and compared between groups with independent t-test or Mann-Whitney U test as appropriate. Categorical variables will be summarized as counts with percentages and compared using the Chi-squared test or Fishers exact test as appropriate. All statistical analyses will be performed with SAS v 9.4

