4.4. ANALYSIS OF THE TERTIARY OUTCOMES

The tertiary outcomes will be calculated as proportions and cumulative incidences with 90%CIs, and medians with IQRs for all the study participants combined and by age group and MISC status

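### SAP 3.3 lists components for the respiratory-support duration that differ from Aim 3c: high-flow nasal cannula is missing and extracorporeal support is added

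*SAP*

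**What the plan says.** Specific Aim 3 in protocol I.B and SAP 1.3 describe Aim 3c in the same words: a median duration of stepped-up respiratory support in hospital, explained as a "new requirement for high-flow nasal cannula, non-invasive ventilation, and/or mechanical ventilation, relative to any at-home baseline requirement".

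SAP 3.3 (Exploratory Outcomes), the list an analyst would program from, gives the outcome as "duration of assisted ventilation (Mechanical ventilation, Non-invasive ventilation and Extracorporeal life support".

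The protocol's outcome section, IV.B, names "cumulative incidence of VTE; and duration of assisted ventilation" and lists no components. Protocol IV.H refers back to IV.B for the tertiary endpoints, not to the wording of the aim. SAP 4.4 fixes only the summary: "medians with IQRs for all the study participants combined and by age group and MISC status". Neither document says which definition governs.

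**The concern.** The SAP holds two definitions of one outcome, in 1.3 and in 3.3, and the one in its outcome list is not the stated aim. If the analysis is programmed from 3.3, a child whose only support is high-flow contributes no time. A child who has high-flow before or after ventilation loses those days. The figure would still be read as the answer to Aim 3c. Respiratory-support duration is one of two clinical efficacy measures in Aim 3 (the other is VTE), and protocol IV.L names respiratory outcomes among the knowledge to be gained. What is at stake is therefore the correct labelling of a reported exploratory result. The safety conclusion does not depend on it.

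**Working it through.** **Definitions side by side.** The documents give no figure to reproduce, so the check starts with the text.

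| Element | Aim 3c (protocol I.B, SAP 1.3) | SAP 3.3 | Protocol IV.B |
|---|---|---|---|
| High-flow nasal cannula | counted | not listed | not stated |
| Non-invasive ventilation | counted | counted | not stated |
| Mechanical ventilation | counted | counted | not stated |
| Extracorporeal life support | not listed | counted | not stated |
| New relative to at-home baseline | required | silent | silent |

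The first and fourth rows are explicit conflicts between component lists. The fifth is a silence. Protocol IV.B is compatible with either list, so it cannot decide between them.

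**What could follow numerically.** The documents do not say how many children had high-flow, home ventilation or extracorporeal support, or for how long. The arithmetic below is therefore conditional and covers the high-flow omission only.

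Inputs and assumptions:
- n = 38, from SAP 2.5 ("The study enrolled 38 participants").
- Children without support enter as 0 days (assumed).
- s = number supported under Aim 3c, and h = number of those whose only support is high-flow. Both are assumed values.

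Median: with n = 38 it is the mean of the 19th and 20th ordered values, so it is 0 once at least 20 children have 0 days.
- Zeros under Aim 3c: 38 − s.
- Zeros under SAP 3.3: 38 − s + h.
- The SAP 3.3 median is 0 when 38 − s + h ≥ 20, that is, when h ≥ s − 18.

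Results:
- s = 24: 14 zeros under Aim 3c, so its median is above 0. With h = 6 there are 14 + 6 = 20 zeros, and the SAP 3.3 median is 0.
- s = 20: h = 2 is enough. s = 28: h = 10 is needed.
- s ≤ 18: at least 20 zeros under both definitions, so both medians are 0 and the omission does not show in the median. This is possible, because the COVID-19 route into the trial asks for "One or more signs and/or symptoms of COVID-19 illness within the past 72 hours", and cough or fever alone would qualify on that criterion.

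Upper quartile: SAP 4.4 also asks for the IQR. SAP 4.1.2 names SAS 9.4. Assuming its default percentile definition, 38 × 0.75 = 28.5, so the upper quartile is the 29th ordered value and is 0 once 29 children have 0 days. With s = 14 there are 24 zeros under Aim 3c, and both medians are 0. With h = 5 there are 24 + 5 = 29 zeros, so the upper quartile is 0 under SAP 3.3 but above 0 under Aim 3c. With s ≤ 9 it is 0 under both.

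These thresholds hold at n = 38. The analysis population in SAP 4.1.1 and the complete-case rule in SAP 4.1.4 may make n smaller. For even n the median condition is h ≥ s − n/2 + 1. With n = 36 and s = 24 it gives 24 − 18 + 1 = 7 instead of 6.

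**The case against.** **SAP 3.3 is shorthand.** Its one sentence shortens all three exploratory outcomes. It also leaves out that the D-dimer limit is for age and that VTE must be confirmed radiologically, both of which SAP 1.3 states. This stands for the baseline condition. A reader might infer that SAP 3.3 removes that condition, so that a child on unchanged home ventilation gains counted days. The documents do not support this: SAP 1.3 still supplies the qualifier, and omission from an abbreviated sentence is weak evidence of a redefinition. The argument does not cover the component list, because abbreviation does not add extracorporeal support.

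**High-flow may fall under non-invasive ventilation.** Aim 3c names the two separately in both documents, so the plan's own wording speaks against this.

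**The looseness begins in the protocol.** This is correct. IV.B and IV.H already use the general label, so the definition is unreconciled across both documents. The list that omits high-flow and adds extracorporeal support appears only in SAP 3.3.

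**Extracorporeal support may change nothing.** This also stands: if it falls within time on mechanical ventilation, the duration is the same.

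**The outcome is exploratory.** It is descriptive and single-arm, and no hypothesis, test or decision rule is attached to it. That limits the weight of the point but does not remove the contradiction.

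**Conclusion.** The point holds as a conflict of definition. SAP 3.3 omits high-flow nasal cannula and adds extracorporeal life support relative to Aim 3c. It is silent on the at-home baseline, and no other section settles the matter. A result programmed from SAP 3.3 alone would not be Aim 3c.

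The size and direction of the effect cannot be computed from the documents, and the effect may be zero. The case of 24 supported and 6 high-flow-only children is an illustration. It rests on all 38 children entering and on unsupported children counting as 0 days.

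A reader might go further and infer a shift of so many days, or a bias in one direction. The documents support neither. If only supported children are summarised, losing high-flow time shortens the durations of ventilated children. Removing high-flow-only children from the group can raise or lower the median, depending on how long their support lasted. The net result depends on frequencies and durations that are not given.

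Nor does SAP 4.4 establish that unsupported children enter as 0 days. That is the plain reading, but the phrase may only contrast the whole group with the subgroups.

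The correction is worth making because it is cheap and restores the plan's own aim. The primary safety analysis is unaffected.

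**What to change.** In SAP 3.3, replace the component list with the Aim 3c definition: high-flow nasal cannula, non-invasive and/or mechanical ventilation, counted only where new relative to any at-home requirement. Align protocol IV.B with it, since IV.H relies on that section. If a duration that includes extracorporeal support is wanted, keep it as an additional outcome under its own name.

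Optionally, add one line to SAP 4.4 saying whether children without support enter the median as 0 days.

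The cost is wording and a few lines of code, plus one more reported line if the additional outcome is kept. No new data are needed if high-flow start and stop dates and at-home support were recorded, as Aim 3c requires. The case report forms are in the Manual of Operations, so this cannot be confirmed from the protocol and SAP. If they were not recorded, chart retrieval for up to 38 children would be needed.

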3.3. OTHER PARAMETERS

- 3.3.1 Demographic and clinical characteristics
- Age, median years
- Gender
- Weight
- BMI
- Complete blood count
 - White blood count
 - Hemoglobin
 - -Platelet

-Coagulation

- -Prothrombin time
- -Partial thromboplastin time
- -International normalized ratio
- -Fibronogen
- -D-dimer
- -Creatinine

3.3.2 Clinical measures

- -COVID-19-related medications
 - -Corticosteroids
- -Nonsteroidal anti-inflammatory
- -Intravenous immunoglobulin
- -Remdesivir
- -Azithromycin
- -Anakinra
- Tocilizumab
- Hospital course
- Length of stay
- -Mortality
- -Central venous catheterization
- Discharged on thromboprophylaxis
- Discharged on aspirin

4. STATISTICAL METHODOLOGY

4.1. GENERAL METHODOLOGY

Data analysis for this study will be performed at the JHAC DCC-PMCS at study completion, once the database has been locked and the Statistical Analysis Plan has been finalized and approved by the study team.

4.1.1. Population for analysis

The population will include all enrolled patients who: 1) had no protocol violations in eligibility criteria; 2) received at least one dose of enoxaparin; and 3) underwent primary outcome determination within 30 days of COVID diagnosis.

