The Schedule of Assessments is shown in Table 1. SAE monitoring and safety laboratory monitoring occurs on days 1-3, and on days 7 and 14 if the patient is still hospitalized. For all participants, pertinent clinical data will be captured as follows: results of coagulation and thrombophilia testing; nature of any major or clinically-relevant non-major bleeding episodes (as defined in Section IV B, above) during the anticoagulant therapy period (with detail as to amount of any related blood transfusion and/or any other intervention required—see also Data and Safety Monitoring Plan section); and nature of any new onset VTE (with detail as to signs/symptoms and anatomic site). PDFs of the REDCap electronic case report forms (eCRFs), as well as SAE report forms, are provided in the Manual of Operations. All SAEs and enoxaparin regimen adherence will be tracked

throughout hospitalization, and SAEs will continue to be tracked through 30 days postenrollment.

Children will complete their participation in the trial at the 30 days (+/- 2 days) postenrollment end-of-study telephone visit. As noted previously, the primary safety endpoint collection also occurs at the 30 days (+/- 2 days).

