# E. Description of Population to be Enrolled

#### 1. Target Enrollment

The target accrual is based on the primary endpoint (safety). The safety population is defined as all patients who received at least one dose of the enoxaparin regimen. In order to achieve adequate power and precision for determination of safety in the primary analysis (see also section G, below), the target enrollment is 38 evaluable children, from among a total of 12-15 participating sites. Participants who do not received at least one dose of the enoxaparin regimen (i.e. early termination, withdrawal of consent) will be replaced. Anticipating an 85% retention rate, we will enroll up to 45 participants. Both males and females of all races and ethnic groups are eligible for this study.

Table 1. Schedule of Assessments.

Assessment	Screening (Within 72 hours of hospital admission)	Enrollm ent Day 0	Day 1	Day 2	Day 3 *	Day 7 *	Day 14 *	Day 30 (+/- 2 days)
Informed consent		Х						
Enrollment		Х						
Full H&P	Х							
Focused H&P			Х	Х	Х	Х	Х	
Weight	Х							
CBC with platelet count	Х				Х	Х	Х	
PT and aPTT 	Х				Х	Х	Х	
Fibrinogen 	Х				Х	Х	Х	
Serum creatinine	Х				Х	Х	Х	
Urine pregnancy screen 	Х							
Research blood specimen 		Х	Х	Х	Х	Х	Х	
Anti-factor Xa level 			Х	+/- X				
SAE Monitoring			Х	Х	Х	Х	Х	Х
Bleeding event (based on focused interim H&P)			Х	Х	Х	Х	Х	Х
VTE event (based on focused interim H&P, with radiological confirmation when suspected clinically)			х	х	х	х	х	х
Telephone visit 								Х

Obtained for research purposes if not already being obtained clinically.

 For participants <20kg: (1) 3ml blue top tube and (1) 4mL CPT Tube (7mL total). For participants  $\ge$ 20kg, (1) 3mL blue top tube and (2) 4mL CPT tubes (11mL total). Research blood collection is for central research lab testing of D-dimer, Clot Formation and Lysis (CloFAL) assay, IL-6, and anti-SARS-CoV-2 IgG, as well as banking plasma, DNA isolated from the buffy coat, and peripheral blood mononuclear cells (PBMCs) for future research.

 Obtained at 4 hours after 1st or 2nd dose of enoxaparin, at initial dosage (mg/kg) and any subsequent change in dosage.

Focused, scripted assessment of symptoms of potential concern for bleeding events, VTE events, and SAEs. Refer to Manual of Operations.

\* If still hospitalized.

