# H. Data Analysis Plan:

The statistical analysis plan was developed by the lead trial biostatistician. Subject demographics and characteristics at study entry will be summarized with counts and percentages for categorical variables, and with means, standard deviations, medians, and interquartile ranges (IQR) as appropriate, for numeric variables. Missing data will not be imputed. Analysis of the primary endpoint will be conducted on the safety population, which includes all subjects who receive at least one dose of enoxaparin. The primary endpoint, cumulative incidence of ISTH-defined [11] clinically-relevant bleeding events during hospitalization, will be calculated with the corresponding exact (Clopper-Pearson) 90% confidence intervals (90%CIs). The precision of estimates for different cumulative incidences of clinically-relevant bleeds and corresponding 90% Cis are as follows: 0/38, 0% (0-7.6)%; 1/38, 2.6% (0-11.8%); 2/38, 5.3% (0-15.7%). The secondary endpoint, twice-daily enoxaparin dose required to achieve target anti-Xa levels, will be summarized

with medians and IQRs for all the study participants combined and by age group. Medians will be compared across age groups, if there are adequate numbers in the groups, using the Kruskal-Wallis test and a *post-hoc* Bonferroni-adjusted Mann-Whitney U test, if needed. The tertiary endpoints (as outlined in Section IV.B) will be calculated as proportions and cumulative incidences with 90%CIs, and medians with IQRs.

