# 2. Protocol Stopping Criteria

Following its review of the DSMB Report and any other relevant data at each meeting, the COVAC-TP independent DSMB will make recommendations to the Steering Committee and the NHLBI Office of the Director regarding termination vs. continuation of the phase 2 clinical trial as noted in Table 2. These recommendations by the DSMB will consider the stopping rules and cumulative SAE profile to date and other relevant safety findings in the study, as well as trial quality and enrollment metrics. In the case of persistently poor trial enrollment metrics, the DSMB may recommend termination of the trial for futility, versus continuation of the trial with protocol modifications.

Reasons for early termination are as follow:

- Evidence of safety concerns—although stopping rules have been established as a guide, this can occur at any point during the study, based on the DSMB's review of cumulative data to date at scheduled or *ad hoc* DSMB meetings.
- Determination of futility: Evidence of persistently poor trial enrollment metrics, which cannot be (or has not been) remedied via protocol modification or other appropriate corrective action.

# Patients who Received Enoxaparin Thromboprophylaxis	Pause if # of Patients with Clinically-Relevant Bleeding				
<10	1				
10-<20	2				
20-<30	3				
30-<38	4				

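### SAP 4.1.1 adds two conditions to the protocol's all-dosed safety population, so a child who received enoxaparin can be left out of the primary bleeding estimate

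*SAP*

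**What the plan says.** Protocol IV.E.1 (Target Enrollment) gives the definition: "The safety population is defined as all patients who received at least one dose of the enoxaparin regimen". Protocol IV.H (Data Analysis Plan) applies it: "Analysis of the primary endpoint will be conducted on the safety population, which includes all subjects who receive at least one dose of enoxaparin". The pause rule in Protocol IV.J.2, Table 2, uses the same kind of denominator, headed "Patients who Received Enoxaparin Thromboprophylaxis". On timing, Protocol IV.D counts from enrollment and states that "the primary safety endpoint collection also occurs at the 30 days (+/- 2 days".

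SAP 4.1.1 sets three conditions. One, at least one dose, is the protocol's. The other two are added: the child "had no protocol violations in eligibility criteria", and the child "underwent primary outcome determination within 30 days of COVID diagnosis". No other population appears in the SAP, and SAP 4.2 names none for the primary outcome. SAP 4.5 nevertheless states its precision for 38 patients in a safety population, a term the SAP does not define.

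On numbers, SAP 2.5 reports 38 enrolled. The protocol replaces undosed children only: "Participants who do not received at least one dose of the enoxaparin regimen (i.e. early termination, withdrawal of consent) will be replaced".

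**The concern.** A child who was enrolled in error but dosed was still exposed to the drug and can still bleed. For a safety endpoint the exposed children are the natural denominator, and the protocol chose them. The SAP instead applies a per-protocol type of filter. The protocol mentions a per-protocol analysis only in a footnote on major deviations (IV.J.4) and does not make it primary.

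At stake is agreement between monitoring and reporting. A bleed could count toward the Table 2 pause rule and then be missing from the primary estimate. With 38 children and few expected events, one removal can be visible in the result.

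**Working it through.** **1. The plan's own precision figures.** Inputs: n = 38 and x = 0, 1 or 2 bleeds (Protocol IV.H, SAP 4.5). The exact two-sided 90% upper limit is the 0.95 quantile of Beta(x + 1, n − x). For x = 0 this is 1 − 0.05^(1/n), so 1 − 0.05^(1/38) = 7.58%. For x = 1 it is 11.89%, and for x = 2 it is 15.66%. The documents print 7.6%, 11.8% and 15.7%, so they agree to within 0.1 point.

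**2. One dosed child removed.** Who is removed is an assumption. Any such removal takes the denominator below 38, because 38 were enrolled and dosed children are not replaced.

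| Bleeds among 38 | All dosed (upper limit) | Bleeder removed | Event-free child removed |
|---|---|---|---|
| 0 | 0/38 = 0% (7.6%) | not applicable | 0/37 = 0% (7.8%) |
| 1 | 1/38 = 2.6% (11.9%) | 0/37 = 0% (7.8%) | 1/37 = 2.7% (12.2%) |
| 2 | 2/38 = 5.3% (15.7%) | 1/37 = 2.7% (12.2%) | 2/37 = 5.4% (16.1%) |

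Removing a bleeder lowers the rate by about 2.6 points and the upper limit by 4.1 points (one bleed) or 3.5 points (two bleeds). Removing an event-free child raises the rate by about 0.1 point and the limit by 0.3 to 0.4 point.

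**3. How likely the large shift is.** If removal is unrelated to bleeding, one removed child is the bleeder with probability 1/38 = 2.6% (2/38 = 5.3% with two bleeds). If the true rate were 2.6%, the chance of no bleeds at all would be (1 − 0.026)^38, about 37%. In that case the rate cannot change.

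**4. The time condition.** This step rests on three assumptions: diagnosis is the date of the positive test, determination is the day-30 telephone call, and the test window in the inclusion criteria ("Positive nucleic acid test, antigen testing, or antibody testing for SARS-CoV-2 within the past 7 days") is counted back from enrollment. Let d = 0 to 7 be the days from test to enrollment and v = 28 to 32 the day of the call. The condition is d + v ≤ 30:

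- d = 0: calls on days 28, 29 and 30 qualify; days 31 and 32 do not.
- d = 1: days 28 and 29 qualify.
- d = 2: day 28 only.
- d = 3 to 7: no day qualifies.

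The d = 0 row separates the two changes. There diagnosis and enrollment coincide, yet days 31 and 32 still fail, because the SAP has dropped the protocol's allowance after day 30. Moving the origin back to enrollment alone would not restore those two days.

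The multisystem inflammatory syndrome route lists a known exposure and no positive test, so this grid does not cover children who enter that way. The SAP does not say what their diagnosis date is.

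**The case against.** The strongest defence is that 4.1.1 is loosely drafted. SAP 2.5 and 4.5 together (38 enrolled, 38 in the safety population) fit a reading in which every enrolled child was dosed and the protocol's population was meant all along. That is plausible, but 4.1.1 then conflicts with the SAP's own precision statement and still needs correcting.

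Three further points stand in part:

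- Neither document imputes (Protocol IV.H, SAP 4.1.4), so a child with no outcome might drop out in any case. That covers missing outcomes, but not the eligibility condition or the changed time limit.
- Table 1 of the protocol has bleeding checked on days 1 and 2, and on days 3, 7 and 14 if the child is still in hospital. If the hospital record is the determination, the time condition removes few or no children.
- A removed bleed would not vanish from the trial. Clinically relevant bleeds are serious adverse events of particular interest and are centrally adjudicated (Protocol IV.J.3). The SAP also plans a flow figure with exclusions (4.1.2) and a tabulation of violations and withdrawals (4.1.5). The loss would be from the primary estimate, not from the safety record.

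A reader might also infer that one removal decides Hypothesis 1, which is set at the printed figures for 1/38 (2.6%, upper limit 11.8%). One removal can indeed put a one-bleed result on either side of those figures. But neither analysis section attaches a test or decision rule to them, and the printed 11.8% is itself slightly below the exact 11.89%.

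**Conclusion.** The contradiction is certain. The protocol analyses all dosed children, and the SAP's only population is narrower by two stated conditions. The second of these changes both the time origin and the allowance after day 30.

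The effect is conditional. In the illustration, removing one bleeder moves the rate by about 2.6 points and the upper limit by about 3.5 to 4.1 points. Removing one event-free child, or any child when nobody bled, hardly moves either. The figures assume 38 dosed children and a single removal. The finding that children tested 3 to 7 days before enrollment cannot qualify holds only under the three timing assumptions.

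A reader might infer that children were removed, or that the reported bleeding rate is too low. The documents support neither: they show no exclusion, give no count, and leave the direction of any bias unknown. The SAP wording should be corrected.

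**What to change.** - For Aim 1, replace the set in SAP 4.1.1 with the protocol's safety population, all participants with at least one dose. Define that term in the SAP so that the 38 in 4.5 refers to it.
- Remove the limit counted from diagnosis. If a time limit is kept, use the protocol's day 30 ± 2 from enrollment, so that the allowance is restored as well as the origin.
- Keep dosed children with incomplete follow-up in the safety population and report their number. How their outcome is handled depends on the endpoint window. Protocol IV.A and SAP 3.1 say 30 days, while Protocol IV.H and SAP 4.2 say the hospital stay. These must be reconciled first, because under the 30-day reading a complete-case rule could still remove a child lost after discharge.
- Keep the present 4.1.1 set, if wanted, only as a labelled per-protocol sensitivity analysis.
- In the flow figure already planned in SAP 4.1.2, give the number of dosed children removed by each condition.

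The cost is SAP wording, one optional sensitivity table and a few counts, with no new data. The downside is that a few children with eligibility deviations may remain in the primary estimate.
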